12.2 Participant demographics and other baseline characteristics

Demographic and other baseline data including disease characteristics will be summarized descriptively by treatment group for the FAS.

Categorical data will be presented as frequencies and percentages. For continuous data, the mean, standard deviation, median, minimum, and maximum will be presented.

Relevant medical histories and current medical conditions at baseline, including NASH specific co-morbidities, will be summarized separately by system organ class and preferred term and by treatment group.

12.3 Treatments

The Safety set will be used for the analyses below. Categorical data will be summarized as frequencies and percentages. For continuous data, mean, standard deviation, median, 25th and 75th percentiles, minimum, and maximum will be presented.

The duration of exposure (days) to investigational treatment, the dose intensity (computed as the ratio of actual cumulative dose received and actual duration of exposure) and the relative dose intensity (computed as the ratio of dose intensity and planned dose intensity) will be summarized for the safety set. The proportion of participants with dose reduction will also be presented by treatment groups.

Proportion of participants non-compliance with the planned study treatment, which is defined as relative dose intensity >1.25 or <0.75, will be summarized descriptively for the double-blind treatment period.

Concomitant medications and significant non-drug therapies prior to and after the start of the study treatment will be listed and summarized by treatment group according to the World Health Organization (WHO), Anatomical Therapeutic Chemical (ATC) classification system.

12.4 Analysis of the primary endpoint(s)/estimand(s)

The two primary endpoints to be analyzed are:

1. Whether the participant has at least one stage improvement in fibrosis without worsening of NASH at Week 48 compared with baseline;

2. Whether the participant achieves resolution of NASH and no worsening of fibrosis at Week 48 compared with baseline.

Five pairwise comparisons may be evaluated for each primary endpoint, rendering a total of ten potential comparisons. Family-wise Type I error rate is controlled at two-sided 5% (one-sided 2.5%) level, and is split for the two primary endpoints. Each primary endpoint will have its own branch of tests and may pass its alpha to the other branch from its last two tests.

The main objective of the study is to demonstrate the combination efficacy of tropifexor + licogliflozin over placebo in participants with NASH and stage 2 or 3 fibrosis, so the two combination therapy vs. placebo tests (one for each primary endpoint) will be performed first. Then, for each primary endpoint, the two monotherapies (LJN452 and LIK066) will be compared with placebo after the combination treatment reveals superiority over placebo with

significant evidence. If one of the monotherapy vs. placebo tests succeeds, then it will pass its alpha to the corresponding combination vs. monotherapy test. An alpha recycling graph is presented in Section 12.4.2 to illustrate the test hierarchy.

The following estimand framework is adopted to meet the objective.

- 1. Population: Participants with NASH (using NAFLD Activity Score (NAS) ≥ 4 with at least 1 point each in inflammation and ballooning on the screening histology assessment performed by the central reader) and stage 2 or 3 fibrosis (using NASH CRN fibrosis criteria), as defined by the inclusion and exclusion criteria of the study Section 5.
- 2. Treatment of interest: the combination therapy (tropifexor 140 μ g + licogliflozin 30 mg, once daily) is the treatment of interest in the comparisons of combination vs. placebo, combination vs. tropifexor, and combination vs. licogliflozin, whereas the monotherapy (tropifexor 140 μ g once per day or licogliflozin 30 mg once per day) is the treatment of interest in the comparisons of tropifexor vs. placebo and licogliflozin vs. placebo.
- 3. Variables of interest: histological response defined as:
 - a. Whether the participant achieves improvement in fibrosis by at least one stage without worsening of NASH at week 48 compared with baseline.
 - b. Whether the participant has resolution of NASH (absence of ballooning with no or minimal inflammation by histology) and no worsening of fibrosis at week 48 compared with baseline.
- 4. Summary measure: Odds ratio of participants achieving histological response at Week 48 for the following comparisons for each primary endpoint: combination vs. placebo, monotherapies vs. placebo, and combination vs. monotherapies.
- 5. Intercurrent events include
 - > Early discontinuation of study treatment before week 48 visit.
 - Non-histologic clinical event suggesting treatment failures (e.g bariatric surgery, liver transplant and death due to disease).
 - > Study treatment incompliance defined as relative dose intensity >1.25 or <0.75.
 - More than four weeks of cumulative exposure to any prohibited medications Section 6.2.2, alcohol usage more than what is permitted in the protocol, initiation of other T2DM or lipid lowering medication (e.g. GLP-1 modulator, statins), initiation of other treatment being evaluated or approved for NASH, or new concomitant interventions for weight control before the assessment for primary endpoint. The identification of relevant medications will be based on ATC3 and/or ATC5 codes, which will be included in analysis data set specifications. The list of concomitant interventions with significant effect for general weight loss will be determined based on blinded review of the study data.

For the intercurrent events related to the primary estimand, various strategies (such as treatment policy and composite variable) defined in ICH E9 (R1) will be utilized for the analyses. For instance, participants who discontinue the treatment after Week 24 will be asked to have their biopsies assessed at Week 48 regardless of the intercurrent event (treatment policy strategy), participants who discontinue the treatment before Week 24 will be considered as non-responders (composite variable strategy), and participants who have no biopsies extracted at Week 48 will be considered as non-responders (composite variable strategy).

Novartis	Confidential	Page 135 of 160
Amended Protocol Version 02 (Clean)		Protocol No. CLJN452D12201C

For non-intercurrent event missing data, certain multiple imputation methods will be applied to estimate the endpoints.

12.4.1 Definition of primary endpoint(s)/estimand(s)

Section 2.1 describes the primary estimands that contain the primary endpoints. This section defines the primary endpoints in detail.

The study uses two primary endpoints.

The first primary endpoint is: Whether (yes or no) the participant achieves improvement in fibrosis by at least one stage without worsening of NASH at week 48 compared with baseline.

One stage fibrosis improvement is defined as the decrease by one point on the NASH CRN fibrosis score, i.e. "from 3 to 2" or "from 2 to 1" (considering that the randomized participants either has stage 2 or stage 3 fibrosis at baseline). Worsening of NASH is determined if any of three components of the NAS score (Steatosis, Lobular inflammation or Hepatocyte ballooning) at Week 48 is greater than that at baseline (FDA definition).

The second primary endpoint is: Whether (yes or no) the participant has resolution of NASH and no worsening of fibrosis at week 48 compared with baseline.

[figure not shown]
Resolution of NASH is satisfied if the NAS score for lobular inflammation ≤ 1 AND the NAS score for Hepatocyte ballooning = 0, regardless of the value for steatosis (FDA definition). Worsening of fibrosis is defined as an increase in the NASH CRN fibrosis score from baseline to Week 48, i.e. "from 2 to 3", "from 2 to 4", or "from 3 to 4".

The two binary primary endpoints will be summarized as odds ratios for pairwise comparisons between treatments.

12.4.2 Statistical model, hypothesis, and method of analysis

The main goal of the study is to reveal the efficacy of the combination therapy (tropifexor + licogliflozin) compared with placebo in the two primary endpoints, so the two tests of combination therapy vs. placebo (one for each endpoint) will be conducted first. The study will be considered successful if at least one of these two tests passes with statistical significance. An overall two-sided 5% (one-sided 2.5%) alpha is adopted to the study and is splitted evenly to the two primary endpoints. In addition to the comparison between combination therapy and placebo, another four pairwise comparisons may be evaluated for each primary endpoint, rendering a total of ten ([1+4]*2=10) potential comparisons. Each primary endpoint will have its own branch of tests and may pass its alpha to the other branch from its last two tests. Under each branch, the two monotherapies (LJN452 and LIK066) will be compared with placebo after the combination treatment shows superiority over placebo with significant evidence. If one of the monotherapy vs. placebo tests succeeds, then it will pass its alpha to the corresponding combination vs. monotherapy test. An alpha recycling graph (Bretz et al 2009) is presented in Figure 12-1 below to illustrate the test relationship.

Figure 12-1 An alpha recycling graph

Within each primary endpoint branch, five comparisons may be evaluated in the following levels:

- Combination vs. placebo
- Tropifexor (LJN452) vs. placebo; licogliflozin (LIK066) vs. placebo
- Combination vs. tropifexor (LJN452);
- Combination vs. licogliflozin (LIK066);

Since there are two primary endpoints, a total of ten comparisons may be tested.

The comparisons are based on the four arms of the study: one combination therapy arm, two monotherapy arms and one placebo arm. The proportions of histological responders in these four arms are assumed following binomial distributions (n, p). The sampling distribution of the difference $\hat{p}_{m_{_i}} - \hat{p}_{m_{_j}}$ will be asymptotically normal with mean $p_{m_{_i}} - p_{m_{_j}}$ and variance $\frac{p_{m_i}(1-p_{m_i})}{n_{m_i}} + \frac{p_{m_j}(1-p_{m_j})}{n_{m_j}}$, where *m* is the index of the primary endpoint (m = A if the

Novartis	Confidential
Amended Protocol Version 02 (Clean)	

endpoint is "at least one stage improvement in fibrosis without worsening of NASH". m = B if the endpoint is "NASH resolution without worsening of fibrosis".), and *i* & *j* are the indices of the two treatments in the comparison. For example, in the first level tests, *i* represents the combination treatment and *j* denotes the placebo. The information of proportion difference is later used for sample size calculation.

Some additional notations:

 $p_A = (p_{A_Cmb}, p_{A_LIK}, p_{A_LJN}, p_{A_Plc}) \sim$ True (population-wise) response rates of combination, licogliflozin, tropifexor and placebo with respect to at least one stage improvement in fibrosis without worsening of NASH at Week 48.

 $p_B = (p_{B_Cmb}, p_{B_LIK}, p_{B_LJN}, p_{B_Plc}) \sim$ True (population-wise) response rates of combination, licogliflozin, tropifexor and placebo with respect to NASH resolution without worsening of fibrosis at Week 48.

 $n_A = (n_{A_Cmb}, n_{A_LIK}, n_{A_LJN}, n_{A_Plc}) \sim$ Numbers of participants in the combination, licogliflozin, tropifexor and placebo arms to be analyzed for primary endpoint A.

 $n_B = (n_{B_Cmb}, n_{B_LIK}, n_{B_LJN}, n_{B_Plc}) \sim$ Numbers of participants in the combination, licogliflozin, tropifexor and placebo arms to be analyzed for primary endpoint B.

 $\hat{p}_A = (\hat{p}_{A_Cmb}, \hat{p}_{A_LIK}, \hat{p}_{A_LJN}, \hat{p}_{A_Plc}) \sim \text{Observed response rates of the combination,}$ licogliflozin, tropifexor and placebo arms with respect to at least one stage improvement in fibrosis without worsening of NASH at Week 48.

 $\hat{p}_B = (\hat{p}_{B_Cmb}, \hat{p}_{B_LIK}, \hat{p}_{B_LJN}, \hat{p}_{B_Plc}) \sim \text{Observed response rates of the combination,}$ licogliflozin, tropifexor and placebo arms with respect to NASH resolution without worsening of fibrosis at Week 48.

The null and alternative hypotheses of the ten comparison tests can be represented in the following form of odds ratio:

$$H_{m_k_0} \colon \frac{p_{m_i} \, (1-p_{m_i})}{p_{m_j} \, (1-p_{m_j})} = 1 \ \text{ vs. } H_{m_k_1} \colon \frac{p_{m_i} \, (1-p_{m_i})}{p_{m_j} \, (1-p_{m_j})} \neq 1 \ ,$$

where m, k, and i&j are the indices of the endpoint, the test, and the compared populations, respectively. For instance, if the endpoint to be analyzed is "whether the participant achieves improvement in fibrosis by at least one stage without worsening of NASH at week 48 compared with baseline", then m = A and the five relevant comparisons are:

Combination vs. placebo (test 1, k = 1, i = Cmb, j = Plc)

Tropifexor (LJN452) vs. placebo (test 2, k = 2, i = LJN, j = Plc); licogliflozin (LIK066) vs. placebo (test3, k = 3, i = LIK, j = Plc)

Combination vs. tropifexor (LJN452) (test 4, k = 4, i = Cmb, j = LJN); combination vs. licogliflozin (LIK066) (test 5, k = 5, i = Cmb, j = LIK)

There are ten potential tests to be performed for the two primary endpoints (five for each primary endpoint), and it is important to control the overall Type I error rate for these tests. The alpha recycling graph presented in Figure 12-1 shows how alpha transfers among them. If the data fails to reject the null hypothesis of a test, then the alpha of that test will not be passed to others. This restriction ensures the control of overall Type I error rate. Again, for the primary

Confidential

Amended Protocol Version 02 (Clean) Protocol No. CLJN452D12201C endpoints, the overall alpha is set at two-sided 5%. A logistic regression model with the logit of probability for histological response as the dependent variable, treatment groups as the main effect, baseline fibrosis stage and T2DM (No/Yes) as explanatory variables, and the baseline BMI as a covariate will be utilized to test the hypotheses at each step. While this model will be the typical logistic regression in most cases, it should be set as the Firth logistic regression if some arm (such as the placebo) has a low response rate, as the Firth method returns less biased results for data with rare events. The null hypothesis of *k*th test, if executed, will be rejected if the p-value for the coefficient of treatment effect in the *k*th comparison is less than or equals to its corresponding alpha. If no alpha is passed to a specific comparison, then its corresponding test will not be performed and p-value will not be calculated. More statistical specifications of the model will be described in the statistical analysis plan (SAP).

The number and percentages of histological responders at week 48 in FAS will be summarized by treatment groups. The difference between the treatment of interest and the alternative treatment will be presented along with 95% confidence interval calculated based on the normal approximation for distribution of the difference between two binomial random variables.

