If the answer to the primary question is yes, additional questions may be assessed:

Does the monotherapy (tropifexor OR licogliflozin) alone, taken once per day by participants with NASH and stage 2 or 3 fibrosis over 48 weeks, result in histologic improvement compared with placebo?

If the answer to this question is yes as well, then another question will be evaluated:

Does the combination therapy lead to more histological improvement than monotherapies?

For each primary estimand, the population, endpoint, and summary measure for the additional questions are the same as those for the primary question. Only the treatment will change accordingly. For the first additional question, the treatment of interest would be monotherapy and the control would be placebo, whereas for the second additional question, the treatment of interest would be combination therapy and the control would be monotherapy.

Intercurrent events of primary estimand will be addressed with various strategies (considering that these events occur before the histological assessments at Week 48):

- 1. Bariatric surgery: participants who have undergone bariatric surgeries during trial participation are considered as non-responders (composite variable strategy).
- 2. Use of alcohol above protocol permitted amount: the intercurrent events (overuse of alcohol) will be ignored for estimation (treatment policy strategy).
- 3. Addition or removal of any medication that may have a confounding effect on the endpoints: the treatment effect will be assessed with the intercurrent event ignored (treatment policy strategy); in the supplementary analysis, the treatment effect will be imputed as if the intercurrent event doesn't occur (hypothetical strategy)
- 4. Premature discontinuation of study treatment due to tolerability, efficacy, adherence, or adverse event: participants who discontinue the treatment after Week 24 will be asked to have their biopsies assessed at Week 48 regardless of the intercurrent event (treatment policy strategy), participants who discontinue the treatment before Week 24 will be considered as non-responders (composite variable strategy), and participants who have no biopsy extracted at Week 48 will be considered as non-responders (composite variable strategy).
- 5. Death, transplantation and other clinical outcomes: participants will be considered as non-responder (composite endpoint strategy).

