4.1 Rationale for study design

NASH is a complex disease with the involvement of multiple pathways. Combination therapy with tropifexor (multimodal effect with anti-steatotic, anti-inflammatory and anti-fibrotic properties) and licogliflozin (weight loss through calorie wasting from gut and kidney, better glycemic control, decrease in de novo liver lipogenesis) is expected to result in greater efficacy and higher number of responders than monotherapy. Each drug works through a different mechanism of action, thus allowing potential additive or complementary beneficial effects.

This study is designed as a randomized, double-blind, parallel-group, multi-center, fixed-dose, phase 2 study to assess the efficacy, safety and tolerability of the combination of tropifexor and licogliflozin and each compound as monotherapy compared to placebo as well as the combination therapy compared to each monotherapy, in participants with NASH F2-F3. The primary endpoint is histology-based (whether the participant achieves resolution of NASH and no worsening of fibrosis, OR improvement in fibrosis by at least one stage with no worsening of NASH at Week 48 compared to Baseline). With supportive key secondary histology endpoints and with acceptable safety and tolerability, this study will inform further development of the combination in NASH participants (i.e. this is a Phase 3 enabling study).

Novartis	Confidential	Page 67 of 160
Amended Protocol Version 02 (Clean)		Protocol No. CLJN452D12201C

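### Combination vs monotherapy is formally tested only after that monotherapy beats placebo; error control does not need this precondition, and under Table 12-3 rates it cuts the chance of any such rejection on the primary endpoints from about 16% to about 0.2%

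*Protocol*

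**What the plan says.** Protocol 12.4.2 gives each primary endpoint its own branch: "An overall two-sided 5% (one-sided 2.5%) alpha is adopted to the study and is splitted evenly to the two primary endpoints". Each branch therefore starts at two-sided 0.025 with combination vs placebo. The next step is: "Under each branch, the two monotherapies (LJN452 and LIK066) will be compared with placebo after the combination treatment shows superiority over placebo with significant evidence". Then: "If one of the monotherapy vs. placebo tests succeeds, then it will pass its alpha to the corresponding combination vs. monotherapy test". Without alpha there is no test: "If no alpha is passed to a specific comparison, then its corresponding test will not be performed and p-value will not be calculated".

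The reason given for error control is general: "If the data fails to reject the null hypothesis of a test, then the alpha of that test will not be passed to others". Recycling between endpoints is limited: "Each primary endpoint will have its own branch of tests and may pass its alpha to the other branch from its last two tests".

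Section 2.1 sets the same order as a chain of questions. The last, asked only after a yes on monotherapy vs placebo, is "Does the combination therapy lead to more histological improvement than monotherapies". Section 4.1 justifies the design by saying that the combination "is expected to result in greater efficacy and higher number of responders than monotherapy". Tables 12-4 and 12-5 give power for combination vs placebo only.

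**The concern.** The same monotherapy arm has to do two opposed things. It must look good enough to beat placebo and then poor enough to lose to the combination. The precondition blocks the formal comparison when the single agent looks weak, although a combination advantage over that component would then be easiest to show. Whether the combination beats its components is one of the trial's stated questions and part of its rationale, and section 12.8 does not show how the testing order affects it. If the order bought error control, the loss might be a fair price. It does not.

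**Working it through.** **Inputs.** Table 12-3: endpoint A (fibrosis improvement) combination 35%, each monotherapy 30%, placebo 20%; endpoint B (NASH resolution) 25%, 20%, 10%. Section 12.8.1: participant-level correlation +0.5; arms 140 (combination) and 80, 80, 80; z-tests of proportions without continuity correction. Section 12.4.2: two-sided 0.025 per endpoint. Assumption: each monotherapy gets half of that, 0.0125 (critical value 2.498).

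**Reproducing the plan.** With z = (p1 − p2) / √[p1(1−p1)/n1 + p2(1−p2)/n2], simulation gives 0.851 for combination vs placebo on at least one endpoint (Table 12-5: 0.85). At 95 per arm it gives 0.547, 0.715 and 0.801 (Table 12-4: 0.55, 0.72, 0.80). A pooled variance gives 0.80 at 140:80:80:80, so the unpooled form is the one that matches. The 50:110:110:110 row agrees less closely (0.605 against 0.62).

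**Hand bound for the plan as written.** Alpha leaves a branch only after a combination vs monotherapy rejection, so recycling cannot help the first one. To win, both M − P and C − M must exceed 2.498 standard errors, so C − P must exceed the sum of the two margins.

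- Endpoint A. Variances: C 0.35×0.65/140 = 0.001625; M 0.30×0.70/80 = 0.002625; P 0.20×0.80/80 = 0.002. SE(M−P) = 0.0680, SE(C−M) = 0.0652, SE(C−P) = 0.0602. Required C − P: 0.170 + 0.163 = 0.333, against an assumed 0.15. z = (0.333 − 0.15)/0.0602 = 3.03; probability 0.0012.
- Endpoint B. Variances: 0.001339, 0.002, 0.001125. SEs 0.0559, 0.0578, 0.0496. Required C − P: 0.140 + 0.144 = 0.284, against an assumed 0.15. z = 2.70; probability 0.0035.

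The sum is 0.0047, so the chance is at most about 0.5% in this approximation. The two statistics share the monotherapy arm with opposite sign. Their correlation is −Var(M)/[SE(M−P)·SE(C−M)], which is −0.59 for A and −0.62 for B.

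**Simulation: chance of any combination-over-monotherapy rejection on the primary endpoints.**

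| True rates (A / B) | As written | In parallel |
|---|---|---|
| Table 12-3 | 0.2% | 16% |
| Monotherapies halfway, 25% / 15% | 0.3% | 48% |
| Monotherapies inactive, 20% / 10% | 0.2% | 78% |
| Combination 50% / 40%, rest as Table 12-3 | 24% | 96% |

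Rows two to four are assumed rates. Giving both monotherapies the full 0.025, which bounds any split, yields 1.05% as written under Table 12-3.

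**Error control.** The nulls are equalities (odds ratio 1).

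- If combination truly equals placebo on an endpoint, the first test protects that branch.
- If it does not, a monotherapy cannot equal both, so at most one of {M = P, C = M} is a true null. Testing both at 0.0125 risks no more than 0.0125 per monotherapy, or 0.025 per branch.
- A share moves to the other branch only after both are rejected. If either null was true, an error has already been counted.
- The same holds for superiority claims: M ≤ P and C ≤ M together imply C ≤ P.

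The largest simulated family-wise error over 75 configurations was 0.050 under both procedures. With z-tests on binomial counts both run slightly over: 0.054 as written and 0.054 to 0.056 in parallel, depending on the configurations tried. The unpooled z-test is itself liberal: one combination vs monotherapy test at nominal 0.0125, both rates 50%, rejects about 1.45% of the time. That belongs to the test, not to the order.

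**Other tests.** Both procedures release alpha on the same event, so every decision against placebo is identical trial by trial. Combination vs placebo succeeds in 0.85 and any monotherapy vs placebo in 0.44 under both. Every rejection made as written is also made in parallel.

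**The case against.** The order is a declared choice. Section 2.1 states the chain of questions, and 4.3, 12.4 and 12.4.2 repeat it. Combination vs placebo is the main goal and the sole success criterion, and ranking combination vs monotherapy last is legitimate in a Phase IIb study. This stands. A reader might infer that the protocol mistakes the precondition for an error-control requirement, but it makes no such claim; its stated reason is only that a failed test passes nothing on.

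A reader might also infer that the trial can almost never say whether the combination beats its components. The documents do not support that. Only the formal test and p-value are withheld: the last paragraph of 12.4.2 reports differences with 95% intervals and states no precondition, and 12.4 names the combination as the treatment of interest against each monotherapy. The key secondary endpoint also has its own branch at two-sided 0.05 (Table 12-1).

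The 0.2% is conditional on a 5-point add-on. As written, the chance is 2.2% for combination rates of 40%/30%, 9.9% for 45%/35%, 24% for 50%/40%, and 63% for 50%/40% with placebo at 12%/8%. The parallel procedure does better in every case, but the gap is not always so extreme. The small add-on is itself a main cause of low power, as the 16% shows.

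Finally, two tests holding the same alpha cannot be drawn in a standard Bretz graph. That is true, and the remedy must include a written justification.

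**Conclusion.** The precondition is real, is not needed for family-wise error control, and costs formal combination-over-component evidence without protecting any other test. On the primary endpoints, under Table 12-3 rates and an even split, the chance of such a rejection is about 0.2% as written (at most about 1% for any split) and about 16% in parallel. The gap widens if the monotherapies are weak (0.2% against 78% if inactive) or the add-on is large (24% against 96%). The comparison stays underpowered at a 5-point add-on after the change. The key secondary branch inherits the structure but is not quantified, since the documents give no response rates for it. This is an avoidable inefficiency that should be changed, not a flaw in error control or in the main test.

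**What to change.** In 12.4.2, once combination vs placebo is rejected on an endpoint, test monotherapy vs placebo and combination vs that monotherapy in parallel for each monotherapy. Both use that monotherapy's alpha share (0.0125 if split evenly), and the share passes to the other branch only when both are rejected. Beside Figure 12-1, add one line: once combination differs from placebo, at most one of monotherapy = placebo and combination = monotherapy can be a true null (Shaffer-type logical restriction within closed testing). Align the question order in 2.1, the summaries in the protocol synopsis and 12.4, and the key secondary branch.

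The exact structure matters. Splitting the branch alpha four ways (0.00625 each) would lower the chance of any monotherapy vs placebo rejection from 43.9% to 34.3%; putting combination vs monotherapy first in the same chain would lower it to 0.2%. The parallel form has neither cost.

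The cost is protocol and SAP wording and an annotated figure before unblinding. The supplied SAP describes the three-arm design without placebo, so its testing section has to be rewritten in any case. Section 12.8 should also state the power for combination vs monotherapy, so that its limits are visible.
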